6.7 Visit 6: 1-week follow up

- After 1 week – and within 2 weeks of Visit 5, the patient will be contacted by a research staff member over the phone. Research staff will administer the QIDS and SAFTEE in addition to checking the patient's seizure log.

6.8 Visit 7: 1-month follow up

- 1 month after visit 5 (+/- 2 weeks), the patient will return to DHMC for a follow up with the study neurologist for history and physical, and medication review. Seizure log will be reviewed.
- The patient will have the SAFTEE, QIDS, and MoCA administered by research staff.
- Neuropsychological testing (QOLIE-31, MAC-S, RBANS),
- Dense-array EEG test will be conducted.

6.9 Visit 8: 3-month follow up

- 3 months after visit 5 (+/- 4 weeks), the patient will be contacted by a research staff member over the phone.
- Research staff will administer the QIDS and SAFTEE in addition to checking the patient's seizure log.

6.10 Visit 9: 6-month follow up

- 6 months after Visit 5 (+/- 4 weeks) the patient will return to DHMC for a follow up with the study neurologist, coordinator, and psychiatrist.
- Research staff will administer the MoCA, QIDS, and SAFTEE. Seizure log will be reviewed.
- Neuropsychological testing (QOLIE-31, MAC-S, RBANS) will be done by research staff.
- Medication review will be done with patient or through review of electronic medical record.
- A dense-array EEG test will be conducted, which may include EEG tasks.

7 Statistical Plan

7.1 Statistical Methods

The study will be closely monitored for safety parameters with stopping rules as defined in Section 8.7. At the conclusion of the study, baseline demographics and clinical characteristics will be summarized with means, proportions and associated standard deviations. For safety, occurrence rates of SAE (seizures or hospitalizations) will be estimated and exact binomial confidence intervals will be formed. Very few if any are expected in this small study. The SAFTEE scale will be compared before and after TMS with independent t-tests based on the individual changes from baseline. The study completion rates will be estimated and compared to the target rate of 80% using exact tests for binomial data.

The secondary outcomes will be measured before and after treatment using dense-array EEG biomarkers and depression scores along with test results during functional MRI and EEG. Paired t-tests will be used to compare *change* in depression severity, memory, executive functioning, quality of life, and social cognition from baseline to endpoint. MRI patterns of activation will be analyzed. Analysis of variance for repeated measures will be used to test task and neuropsychological testing results.

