1.5 Dose Rationale and Risk/Benefits

Low-frequency (LF) TMS refers to TMS delivered at a frequency of 1 Hz or below. Unlike HF TMS, LF TMS can decrease cortical excitability and may have anticonvulsant effects[42]. Low frequency TMS applied to right DLPFC also has an extensive though smaller database supporting its antidepressant efficacy, and comparisons to left HF DLPFC TMS suggest both treatments work equally as well[43, 44]. Surprisingly, LF TMS has not been investigated as an antidepressant treatment in patients with epilepsy, though it would have clear advantages compared to HF TMS including increased tolerability and potentially anticonvulsant effects.

2 Study Objectives

Specific Aim 1: To examine the safety and feasibility of accelerated low-frequency transcranial magnetic stimulation (TMS) to the right dorsolateral prefrontal cortex in patients with epilepsy and comorbid depression.

Hypothesis 1.a. (safety): Treatment will not produce serious adverse events defined as an increase in seizure rate or hospitalization.

Hypothesis 1.b. (safety): Treatment will not be associated with a higher rate of adverse events as measured by a modified Systematic Assessment for Treatment Emergent Events (SAFTEE) given at baseline and immediately post-TMS.

Hypothesis 1.c. (feasibility): At least 80% of participants will complete the study protocol.

Specific Aim 2: To examine the utility of electrophysiological and behavioral profiles as biomarkers of depression correlated with response to treatment with right-DLPFC TMS in patients with epilepsy.

Hypothesis 2a: Changes in dense array EEG based biomarkers of depression (hemispheric frontal alpha power asymmetry, anterior cingulate theta power, and frontotemporal alpha coherence) will correlate with changes in depression scores.

3 Study Design

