7.2 Sample Size Determination

For the primary safety outcomes, we consider the expected upper limit of a one-sided 90% exact confidence interval for the proportion with an SAE based on a sample size of 20. If the underlying rate is 0.05, the upper limit is 0.131. This increases to 0.145 if the underlying rate is 0.10.

For the secondary outcomes comparing baseline to endpoint depression measurements, a two-sided paired t-test with a significance level of 0.05 and a power of 0.90 can detect a difference of .764 standard deviations of the changes from baseline.

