8.1 Definitions

Unanticipated Problems Involving Risk to Subjects or Others

Any incident, experience, or outcome that meets all of the following criteria:

- Unexpected in nature, severity, or frequency (i.e. not described in study-related documents such as the IRB-approved protocol or consent form, the investigators brochure, etc.)
- Related or possibly related to participation in the research (i.e. possibly related means there is a reasonable possibility that the incident experience, or outcome may have been caused by the procedures involved in the research)
- Suggests that the research places subjects or others at greater risk of harm (including physical, psychological, economic, or social harm).

Adverse Event

An **adverse event** (AE) is any symptom, sign, illness or experience that develops or worsens in severity during the course of the study. Intercurrent illnesses or injuries should be regarded as adverse events. Abnormal results of diagnostic procedures are considered to be adverse events if the abnormality:

- results in study withdrawal
- is associated with a serious adverse event
- is associated with clinical signs or symptoms
- leads to additional treatment or to further diagnostic tests
- is considered by the investigator to be of clinical significance

Serious Adverse Event

Adverse events are classified as serious or non-serious. A **serious adverse event** is any AE that is:

- fatal
- life-threatening
- requires or prolongs hospital stay
- results in persistent or significant disability or incapacity
- a congenital anomaly or birth defect
- an important medical event

Important medical events are those that may not be immediately life threatening, but are clearly of major clinical significance. They may jeopardize the subject, and may require intervention to prevent one of the other serious outcomes noted above. For example, drug overdose or abuse, a seizure that did not result in in-patient hospitalization, or intensive treatment of bronchospasm in an emergency department would typically be considered serious.

All adverse events that do not meet any of the criteria for serious should be regarded as **non-serious adverse events**.

Adverse Event Reporting Period

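### The SAE proportion analysed for safety covers only seizure events and hospitalizations, so a non-seizure death, life-threatening event or lasting disability without admission meets Section 8.1 but is not counted

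*Combined protocol and SAP*

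**What the plan says.** Section 7.1 sets out the safety analysis: "For safety, occurrence rates of SAE (seizures or hospitalizations) will be estimated and exact binomial confidence intervals will be formed". The parenthesis is not a list of examples, because Hypothesis 1.a in Section 2 uses a closed definition: "Treatment will not produce serious adverse events defined as an increase in seizure rate or hospitalization". The two differ on the seizure component (any seizure in 7.1, a rise in rate in 1.a) but agree that hospitalization is the only other route.

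Section 7.2 introduces its interval as relating to the primary safety outcomes and describes it as the "expected upper limit of a one-sided 90% exact confidence interval for the proportion with an SAE based on a sample size of 20". It does not say which definition of SAE applies. Section 3.2, which lists the primary endpoints, contains no SAE proportion; its safety items are weekly seizure rate and SAFTEE.

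Section 8.1 is broader. Hospitalization ("requires or prolongs hospital stay") is one of six sufficient criteria. The others are a fatal outcome, "life-threatening", "results in persistent or significant disability or incapacity", a congenital anomaly, and an important medical event. On the last it explains: "Important medical events are those that may not be immediately life threatening, but are clearly of major clinical significance". Its examples begin: "For example, drug overdose or abuse, a seizure that did not result in in-patient hospitalization".

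**The concern.** The same label, SAE, has a wide meaning where events are reported and a narrow one where they are analysed. Followed as written, the analysed proportion would leave out some of the gravest outcomes whenever they are neither a seizure nor an admission.

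Nothing else in Section 7 recovers them. The other safety analysis compares SAFTEE before and after TMS, and a patient who dies contributes no later score. The stopping rules in 8.7, to which 7.1 refers, name worsening depression, seizure increase and other side effects, each at more than three patients; none names death or a life-threatening event.

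The gap is plausible in this population. Patients have epilepsy and a depressive episode with inadequate response to an antidepressant. Section 8.2 foresees a QIDS answer that reports an actual attempt, and the procedure it describes (a further rating scale, notification, documentation, clinician follow-up) does not specify admission. Safety is the study's main objective, and 7.1 expects very few SAEs if any, so a single patient can shape the headline result.

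**Working it through.** **1. Definitions side by side.** Cases are assumed not to involve a seizure unless stated.

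| Event | SAE under 8.1 | Counted under 1.a | Counted under 7.1 |
|---|---|---|---|
| Death outside hospital | yes, explicit | no | no |
| Life-threatening event, no admission | yes, explicit | no | no |
| Lasting disability, no admission | yes, explicit | no | no |
| Suicide attempt, no admission | by inference (life-threatening, or important medical event) | no | no |
| Hospitalization for an adverse event | yes, subject to 8.1's exceptions | yes | yes |
| Fatal seizure | yes | only if counted as a rate increase | yes |
| Habitual seizure, no admission, rate unchanged | 8.1's example suggests typically yes | no | yes, read literally |

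The first three rows establish the point. The last row shows that the three sections also disagree about ordinary seizures.

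**2. The plan's own figures.** Inputs from 7.2: N = 20, one-sided 90% exact limit, underlying rates 0.05 and 0.10. For x patients with an event, the upper limit U(x) is the 0.90 quantile of Beta(x + 1, 20 − x). The expected limit is the sum over x of P(X = x) × U(x), with X ~ Binomial(20, p).

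- At p = 0.05, the terms for x = 0 to 5 are 0.3585 × 0.1087 + 0.3774 × 0.1810 + 0.1887 × 0.2448 + 0.0596 × 0.3042 + 0.0133 × 0.3607 + 0.0022 × 0.4149. With the small remainder, the total is 0.1775. The plan states 0.131.
- At p = 0.10, the same sum gives 0.2408. The plan states 0.145.

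The stated limits do not reproduce. No variant tried at N = 20 (80%, 95% or 97.5% confidence; Wald; Wilson) gives both. That is a separate matter, and nothing below uses those figures.

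**3. Effect of one omitted patient, with seizures counted only as in 1.a.**

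- 0/20: U solves (1 − U)^20 = 0.10, so U = 1 − 0.10^(1/20) = 0.109.
- 1/20: U solves (1 − U)^20 + 20U(1 − U)^19 = 0.10. At U = 0.181 the terms are 0.0184 + 0.0815 = 0.0999, so U = 0.181.
- 2/20: U = 0.245. 3/20: U = 0.304.

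One omitted patient therefore moves the estimate by 1/20 = 0.05. The upper limit moves by 0.181 − 0.109 = 0.072 from a base of none, by 0.245 − 0.181 = 0.064 from a base of one, and by 0.304 − 0.245 = 0.059 from a base of two.

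**4. The same with 7.1 read literally.** Section 4.1 excludes only patients with more than 10 seizures per week, and follow-up runs to 6 months, so many patients could have at least one seizure. The documents give no figure for how many. Taking 6, 10 or 16 of 20 as assumptions, the upper limits are 0.467, 0.662 and 0.910. One further patient could then add at most 0.05 to the estimate, and nothing if that patient had already been counted for a seizure. The contrast between 0/20 and 1/20 thus belongs to the 1.a reading only.

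**The case against.** The strongest reply is that no such event would be lost. All adverse events are recorded under 8.4, serious ones are reported under 8.5, deaths go to the IRB on short timelines under 8.5.1, and 8.8 requires regular review of the number and type of SAEs. An analysis endpoint may also legitimately be narrower than a reporting definition. This stands as a limit on the consequence: the safety record is intact. It does not cure the analysis, because the narrow quantity carries the broad label and 7.2 treats it as primary.

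Three further limits stand. The word primary rests on 7.2 alone, since 3.2 does not list this proportion. A death or life-threatening event that is itself a seizure is already counted under 7.1. The size in step 3 depends on the 1.a reading of the seizure component.

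Two stronger readings are tempting. A reader might infer that 8.1 expressly names a suicide attempt as an SAE. It does not: drug overdose is among its examples, and an attempt qualifies only by inference. A reader might also infer that one omitted event would turn Hypothesis 1.a from supported to not supported. Section 7.1 gives an estimate and an interval with no test, threshold or decision rule, and 1.a concerns what treatment produces, so one event of unassessed cause would not formally refute it.

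**Conclusion.** The concern holds in this form. Hypothesis 1.a and 7.1 define the analysed SAE more narrowly than 8.1, and no other analysis in Section 7 makes up the difference. Non-seizure deaths, life-threatening events and lasting disabilities without admission are SAEs that the analysed proportion omits.

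With 20 patients and seizures counted only through a rate increase, each omitted patient adds 0.05 to the estimate. The one-sided 90% exact upper limit goes from 0.109 to 0.181 if no other event is seen. These sizes assume that all 20 patients enter the safety population and that the omitted patient has no other counted event. What changes is the reported estimate and interval; the plan contains no formal decision that would flip. It still needs correcting before analysis, because the proportion as defined would be wrong for what its label claims, and safety is the main question of the study.

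**What to change.** - **Event definition (Section 2 and 7.1).** Count, once per patient, any SAE meeting 8.1 or an increase in seizure rate. Say in 7.2 that this is the proportion meant, and align 3.2 if it is to be a primary endpoint.
- **Components.** Report death, life-threatening event, hospitalization and seizure-rate increase separately alongside the composite.
- **Seizures.** Reconcile the wording in 7.1, in 1.a and in 8.1's example of a seizure without admission, so that habitual seizures enter the analysis only through the rate component. Without this, adopting 8.1 wholesale could make nearly every habitual seizure an event.
- **Counting window.** Section 8.1 ends general adverse event reporting 30 days after the last treatment and afterwards keeps only events related to seizure frequency or depression; 8.4 adds later SAEs if possibly related. A window consistent with this would be all 8.1 SAEs through 30 days after the last treatment, with later seizure- or depression-related events reported separately.

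The cost is a few sentences across Sections 2, 7 and 8.1. With the window above, the events are already recorded under 8.4, so no new procedure is needed. The SAE rate may come out slightly higher.

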3.2 Primary Study Endpoints

1. Change in weekly seizure rate as assessed by self-report seizure log.
2. Change in significant side effects as assessed by the Systematic Assessment for Treatment Emergent Events (SAFTEE)[50].
3. Feasibility of participation such that 80% of patients will complete the study protocol including all measures, MRI, dense array EEG, and TMS.
4. Correlation of pre and post TMS hemispheric frontal alpha power asymmetry, anterior cingulate theta power, and frontotemporal alpha coherence with changes in depression severity.

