4.1 Inclusion Criteria

Participants will be recruited from the epilepsy patient population within the Department of Neurology at Dartmouth-Hitchcock Medical Center. Screening and baseline evaluations will be performed by a board-certified neurologist and psychiatrist as well as a research coordinator trained to reliably administer structured interviews and rating scales. 20 participants will be recruited with the following initial inclusion criteria:

- Females or males age 18 and older.
- Able and willing to provide informed consent.
- Diagnosis of probable epilepsy (focal or generalized) confirmed by the study neurologist.
- English-speaking
- Not pregnant
- Able to safely undergo MRI (as assessed by MRI safety form).
- Have a family member or friend (proxy) who will be able to bring the patient to the hospital and serve as a safety monitor for two consecutive nights.
- Patients on stable doses of current antiepileptic and antidepressant medications for 1 month.

Once patients fulfill initial inclusion criteria, they will be referred to see the study psychiatrist who along with a research coordinator will determine if patient meets the following further inclusion criteria:

- Diagnosis of a depressive episode of any severity (including, mild, moderate, and severe) by the study psychiatrist (Quick Inventory of Depression Severity-Subject Rated [QIDS] score >6 or Neurologic Disorders Depression Inventory – (NDDI-E) score of > 15).
- Inadequate response to at least one antidepressant medication during the current episode.

Exclusion Criteria

Patients will be excluded if the following criteria are met:

- Significant cognitive impairment (Montreal Cognitive Assessment [MOCA] <23)
- History of other major psychiatric disorders (e.g., schizophrenia, bipolar disorder,) or presence of unstable medical comorbidities, which the investigators agree, will interfere with adherence and/or safety.
- Active substance use disorder that the investigators agree will interfere with adherence and/or safety.
- Actively/imminently suicidal (QIDS item 12 score > 2 or MINI Suicidality module score > 16)
- Greater than 10 seizures per week during 1 month prior to treatment, confirmed by the study neurologist.
- History of stroke, moderate-severe traumatic brain injury or other major neurological disorder, which the study neurologist feels will interfere with adherence and/or safety.

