The study period during which adverse events must be reported is normally defined as the period from the initiation of any study procedures to the end of the study treatment follow-up. For this study, the study treatment follow-up is defined as 30 days following the last administration of study treatment. After 30 days, only adverse events related to an increase in seizure frequency or symptoms of depression will be reported.

Preexisting Condition

A preexisting condition is one that is present at the start of the study. A preexisting condition should be recorded as an adverse event if the frequency, intensity, or the character of the condition worsens during the study period.

General Physical Examination Findings

At screening, any clinically significant abnormality should be recorded as a preexisting condition. At the end of the study, any new clinically significant findings/abnormalities that meet the definition of an adverse event must also be recorded and documented as an adverse event.

Post-study Adverse Event

All unresolved adverse events should be followed by the investigator until the events are resolved, the subject is lost to follow-up, or the adverse event is otherwise explained. At the last scheduled visit, the investigator should instruct each subject to report any subsequent event(s) that the subject, or the subject's personal physician, believes might reasonably be related to participation in this study.

Abnormal Laboratory Values

A clinical laboratory abnormality should be documented as an adverse event if any one of the following conditions is met:

- The laboratory abnormality is not otherwise refuted by a repeat test to confirm the abnormality
- The abnormality suggests a disease and/or organ toxicity
- The abnormality is of a degree that requires active management; e.g. further diagnostic investigation, etc.

Hospitalization, Prolonged Hospitalization or Surgery

Any adverse event that results in hospitalization or prolonged hospitalization should be documented and reported as a serious adverse event unless specifically instructed otherwise in this protocol. Any condition responsible for surgery should be documented as an adverse event if the condition meets the criteria for an adverse event.

Neither the condition, hospitalization, prolonged hospitalization, nor surgery are reported as an adverse event in the following circumstances:

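### Section 7.1 counts seizures where Hypothesis 1.a counts an increase in seizure rate, and primary endpoint 1 (change in weekly seizure rate) has no analysis

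*Combined protocol and SAP*

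**What the plan says.** Section 7.1 gives the safety analysis as: "For safety, occurrence rates of SAE (seizures or hospitalizations) will be estimated and exact binomial confidence intervals will be formed". It adds that hardly any such events are expected.

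Hypothesis 1.a in Section 2 reads: "Treatment will not produce serious adverse events defined as an increase in seizure rate or hospitalization". The first primary endpoint in Section 3.2 is: "Change in weekly seizure rate as assessed by self-report seizure log".

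Section 8.1 has four relevant statements:
- An adverse event "is any symptom, sign, illness or experience that develops or worsens in severity during the course of the study".
- A preexisting condition is "recorded as an adverse event if the frequency, intensity, or the character of the condition worsens during the study period".
- Among the examples of events typically considered serious is "a seizure that did not result in in-patient hospitalization".
- Reporting runs from the first study procedure to 30 days after the last treatment, and then narrows: "After 30 days, only adverse events related to an increase in seizure frequency or symptoms of depression will be reported".

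The exclusion criteria in Section 4.1 remove only patients with "Greater than 10 seizures per week during 1 month prior to treatment, confirmed by the study neurologist". Rule 2a in Section 8.7 stops the study when more than 3 patients have an increase over baseline seizure frequency. It gives no minimum rise, baseline period or comparison window.

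**The concern.** In a cohort with epilepsy, having a seizure and having more seizures than before are different events. Hypothesis 1.a concerns the second, but the parenthesis in 7.1, which an analyst would program from, names the first. Two analysts could take different primary safety proportions from the same logs. In a single-arm study the literal version cannot separate habitual seizures from a treatment effect.

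The missing analysis for endpoint 1 is a separate gap. A proportion of patients with an event does not estimate a change in rate. As written, the method for a primary safety endpoint would be chosen after the data are seen, in an unblinded study.

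**Working it through.** **1. Planning benchmark.** Section 7.2 takes underlying event rates of 0.05 and 0.10 with n = 20 and states one-sided 90% exact upper limits of 0.131 and 0.145. The exact limit is the 0.90 quantile of Beta(x+1, 20−x), which is 0.181 for x = 1 and 0.245 for x = 2. The stated figures are the distances from rate to limit: 0.181 − 0.05 = 0.131 and 0.245 − 0.10 = 0.145. That is a separate matter. Only the planned 5 to 10% is used below.

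**2. Literal reading of 7.1.** The documents give no baseline seizure rates, so these are assumed: Poisson seizures, no TMS effect, r per week. Then P(at least one in d days) = 1 − exp(−r·d/7).

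| r per week | 3 days | 30 days |
|---|---|---|
| 0.05 | 2% | 19% |
| 0.25 | 10% | 66% |
| 1 | 35% | 99% |

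At r = 0.25, for example, 1 − exp(−0.25·3/7) = 0.102 and 1 − exp(−0.25·30/7) = 0.657.

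If some patients are seizure-free, multiply by the share who are not. At 0.25 to 2 per week:
- 10 of 20 with seizures: 5 to 29% (3 days), 33 to 50% (30 days).
- 5 of 20 with seizures: 2.5 to 14% (3 days), 16 to 25% (30 days).

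Over 30 days every case in this step exceeds 10%. Over 3 days some do not.

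**3. Endpoint 1.** The methods in 7.1 are:
- exact binomial intervals for SAEs;
- t-tests for SAFTEE;
- exact tests for completion;
- paired t-tests for depression, memory, executive functioning, quality of life and social cognition;
- repeated-measures analysis of variance for task and neuropsychological results.

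None applies to weekly seizure rate.

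Precision of a before/after rate ratio with equal 4-week windows: with E expected seizures per window, the 95% interval extends by a factor exp(1.96·√(2/E)) each way.
- All 20 patients with seizures: E = 20·4·0.25 = 20 gives 1.86; E = 80 (1 per week) gives 1.36.
- Only 10 with seizures: 2.40 and 1.55.

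**4. Rule 2a, if read as any rise between equal 4-week windows.** Let q be the probability that the later of two independent Poisson(4r) counts is the larger. This gives q = 0.346, 0.428 and 0.450 at r = 0.25, 1 and 2. The rule is met by chance with probability P(Binomial(n, q) > 3), where n is the number of patients who have seizures.

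| n | r = 0.25 | r = 1 | r = 2 |
|---|---|---|---|
| 3 or fewer | 0 | 0 | 0 |
| 5 | 0.052 | 0.111 | 0.131 |
| 10 | 0.475 | 0.686 | 0.733 |

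**The case against.** The strongest reply is that the documents already settle the intent. Hypothesis 1.a, the adverse-event and preexisting-condition definitions, the post-30-day reporting rule and stopping rule 2a all refer to onset, worsening or increase. The remark in 7.1 that almost no events are expected fits that reading too. The line on seizures without admission is a generic example, listed beside drug overdose and bronchospasm. This largely stands. A reader might infer that the plan means to count every habitual seizure as a treatment SAE. The documents do not support that: the parenthesis is probably shorthand, and the figures in step 2 show only what following it literally would do.

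A reader might also say that the safety event has no time window at all. That is true of 7.1 alone, since Section 8.1 supplies a usable 30-day period.

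On rule 2a, a reader might infer that chance is bound to stop the trial. With all 20 patients having seizures, the any-rise calculation does give 95% or more at 0.25 per week and above. But the documents state neither an any-rise rule, nor equal windows, nor a common rate. Seizure decisions elsewhere (Sections 4.2.1 and 8.3) rest on the neurologist's judgement, and Attachment E may define the term.

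None of this supplies the missing method for endpoint 1.

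**Conclusion.** The point holds and should be fixed. The event in 7.1 differs from Hypothesis 1.a, and aligning them is a correction of wording toward an intent that is otherwise clear. Left as it is, the literal event would affect 10% of patients in 3 days and 66% in 30 days at 0.25 seizures a week without any TMS effect. These figures rest on Poisson counts and an assumed rate. The absence of an analysis for primary endpoint 1 is plain from the text and needs no assumption.

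Rule 2a is secondary and conditional. Read as any rise, at 0.25 to 2 seizures a week, it would be met by chance in 5 to 13% of trials if 5 of 20 patients have seizures and in about 47 to 73% if 10 do. It could not be met by chance if at most 3 do. If Attachment E defines the increase, this part reduces to a cross-reference.

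**What to change.** 1. **Event in 7.1.** Replace the parenthesis with: *increase in seizure rate over the patient's own pre-treatment month, or hospitalization*. Count it up to 30 days after the last treatment, as in Section 8.1, and report the two components separately. Describe in-session and atypical seizures separately and keep them out of the event. At 10 seizures a week, a seizure during the 12.5 hours of stimulation (15 × 50 minutes) has a chance probability of 1 − exp(−10·12.5/168) = 52%, so including it would bring habitual seizures back in.

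2. **Endpoint 1.** Add a within-patient comparison of weekly seizure rate, pre-treatment month versus Visit 3 to Visit 7. Use observed days as offset and report a rate ratio with a robust 95% confidence interval. The offset is needed because Visit 7 may move by 2 weeks either way.

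3. **Rule 2a, unless Attachment E already covers it.** Name the pre-treatment month as baseline, and state a comparison window and a minimum rise chosen by the investigators. If Attachment E does define these, refer to it in 7.1 and 8.7. The same definition of an increase should serve item 1, since any rise at all also occurs by chance.

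**Cost.** The changes are wording, one recorded baseline count and one added estimate. The neurologist already confirms the pre-treatment month for eligibility, and the logs are reviewed through Visit 9. There are two downsides. The interval for endpoint 1 will be wide, as step 3 shows. And the log is first issued at Visit 1a with no stated minimum time before Visit 3, so part of the baseline month may be recall set against a prospective log. The report should say how much of it was.
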